2.7. Towards randomised controlled trials (objective 7)

Ultimately any proposed treatment strategies will need to be tested in rigorous randomised controlled trials (RCTs). Based on the knowledge gained from these studies we will suggest a design or designs for such trials, defining patient populations, treatments and endpoints. Such a trial would also include a rigorous health economic assessment. The qualitative element of this project will establish existing views of patients regarding RCTs, and these can be incorporated into the trial design. Furthermore, the findings will enable the production of accurate and targeted patient information.

2.8. Proposed sample size

Formal sample size computations are not appropriate here as the aim is to develop predictive models, not to formally test hypotheses. Experience and heuristic arguments suggest that datasets in excess of 10,000 subjects will be required for this exercise. Rules of thumb for reliable predictive modelling suggest 10-20 events per considered variable. We expect to have around 40 potential variables which with a success rate of 20% would imply a minimum data set of 4000 independent cycles, around 8000 patients given that many patients have multiple cycles and we wish to look at multi-cycle endpoints. The sample size is in practice determined by the need to have a representative set of centres and a long enough time span to capture treatment histories along with computational feasibility, and is well in excess of the minimum numbers above.

3. Study Conduct

3.1. Clinical Data Collation

Data collation will be an iterative process involving close liaison between the project team and contributing centres and overseen by the SAB. Three datasets will be created as detailed in (§2.4)

3.1.1. Routine data

Detailed discussions will take place between the project team and each of the 7 contributing centres listed above (§2.4 1&2). Following these discussions a data collation plan will be drafted detailing

1. The minimal dataset to be collected from every site
2. Any additional site-specific data
3. The time period to be collected for each site (may vary due to logistical issues – e.g. changes of data collection processes/database software)
4. The details of the anonymisation and identification of repeat treatments from the same individuals (see §3.1.3 below)
5. The method of data transfer (email or disk)
6. The formats of each variable and the post-processing necessary to make these consistent across sites
7. Descriptions of the embryo grading systems in use at each site and day of transfer
8. Data checking/validity algorithms
9. The structure of the final analysis database and the processing needed to get each centre's data into the database. This will require careful consideration of the hierarchical structure of the data.

This document will be circulated to the SAB for comments and formal approval (either at a face-to-face meeting or via email).

An initial data extraction (maybe of just a sample of the data) and transfer to the project team will then take place and the processes outlined above tested and any issues resolved and any amendments discussed and approved.

The full data extraction will then take place and the complete database assembled and verified. Such iteration as necessary will take place to resolve any data validity issues. Preliminary logistic regression models will be fitted to the assembled datasets using the minimal set of covariates defined in (a) above and any outliers and discrepancies resolved in consultation with the centres. After this stage the database will be locked.

3.1.3. Anonymisation

No personally-identifiable clinical data shall be sent to or retained by the investigators. All data will be anonymised by the contributing centre. Each patient will be given a unique identifier, *maintaining the same identifier across multiple cycles for the same patient*. The appropriate form of the identifier will be determined separately for each centre depending on the practicalities of data extraction and database capabilities. The numbers allocated

must be such that no one outside the contributing centre can identify the patients, thus a hospital number will not be acceptable, but a reference internal to the database holding the data (eg row number in a patient identifier table) would be suitable. All personal identifiers will be removed prior to transmission of the data to the Chief Investigator for analysis. It is permitted that the centre retains a *temporary* copy of the allocated numbers cross-referenced to patient/cycle identifiers so that problems with the data can be identified and resolved. Any such temporary lists will be destroyed at the end of the data extraction/validation phase of the project.

3.2. Patient Perspective Interviews

Note: The descriptions below refer to "couple" as the unit of investigation. This is not intended to imply that in all cases there will be two partners of opposite sex, and there is no exclusion criterion that refers to the patients relationships. If there are potential participants where the relationship is not that of the majority, or where only one partner wishes to be involved, then these should be handled sensitively and with appropriate tailoring of the invitation letters and information sheets as needed for the individual circumstances.

3.2.1. Recruitment process

Purposive sampling techniques will be employed to ensure maximum diversity of sample to include different female ages, parity, duration of infertility and source of funding (which is related to the number of treatment cycles which the couple receive). The qualitative researcher ([name]) will draw up criteria for the patient characteristics in consultation with clinical investigators. Additionally, patients will be made aware of the study at their 'waiting list' meeting (all potential patients are invited to attend this session prior to commencement of treatment, at which they are given basic information about their treatment). For patients who have not had their initial meeting contact will be by letter, later stage patients will be approached in person by the Study Research Nurse in the clinic setting.

Interviews will take place with patients at 3 key decision-making stages: a) waiting list; b) after the first information meeting and clinical appointment (pre-treatment) and c) after the second cycle of treatment (this time point is to capture the views of "experienced" patients, but as some couples will only receive a single cycle patients who have completed treatment with a single cycle may be included in this group).

a) waiting list patients will be identified by the Research Nurse (who is part of the clinical team) from the waiting list. The Research Nurse will obtain minimal contact details of the selected patients on the waiting list from clinic staff. The Research Nurse will then mail an INVITATION PACK which will include:

1. An invitation letter inviting couples to take part in this study.
2. An information sheet explaining the rationale of the study, the design, and how it will be conducted and managed. The principles of confidentiality, anonymity and privacy have been explained in the participant information sheet.
3. A form to be completed by couples and returned to the researcher stating whether they want to take part in the study, or not, and how they can be contacted. The form will allow for couples to indicate that they would prefer to discuss the study further, with the researcher, prior to making a decision as to whether to take part or not.
4. A stamped addressed envelope will be provided to return the forms stating their decision about participating to the researcher.

All couples who receive an INVITATION PACK will be requested to complete and return a signed form if they are willing to participate in this study.

Those who reply will be contacted directly by the qualitative researcher ([name]) by

telephone/email to discuss the study further. Any queries or concerns may be addressed at this point. An appointment will be made for a mutually convenient time and place if they wish to take part in an interview. Those couples who state that they do not wish to take part, or do not return the form, will not be contacted again about the study.

b) after the first information meeting and clinical appointment (pre-treatment) and c) after the second cycle of treatment:

At the next relevant clinic visit patients will be approached directly by the Research Nurse (who is a member of the clinical team). The Research Nurse will have been fully briefed by the researcher ([name]) regarding the aims and objectives of the study. This will enable them to identify suitable participants at these 2 key treatment phases, so that they can introduce the study to patients. Potential participants will be given the information sheet and letter of invitation (on Hospital notepaper) by the nurse, who will explain the study verbally and answer any questions. Those who are willing will be contacted by telephone a few days later to ascertain if they are interested. Patients and partners will be given as long as the wish to consider participation. Those who express an interest to the Research Nurse will be asked to give contact details so that the research team can make an appointment for interview. The qualitative investigator ([name]). will contact the potential participant by phone to answer any questions and make the practical arrangements for the interview. If the potential participants require further time to consider participation then a second phone call will be agreed. Formal written consent will be recorded at the interview after an additional explanation of the study and a further opportunity to opt out.

All participants:

Immediately prior to the interview the consent will be discussed and signed individual consent forms will be obtained. Couples will be reassured regarding confidentiality and anonymity. A copy of the consent form will be given to the participants. A short demographic questionnaire will be completed prior to the interview which will ask only about those characteristics of importance to this study.

3.2.2. Interview Conduct

In-depth exploratory interviews, employing the conversational style, will be conducted with couples at the three key treatment stages of interest (waiting list; after the first information meeting and clinical appointment; and after the second cycle of treatment). Interviews will be conducted in a setting of the couple's choice (either home or clinic). Travel expenses and refreshments will be provided for those couples who opt for a clinic setting. All interviews will be taped, with permission, and transcribed prior to analysis.

The interview will begin by asking couples to describe their individual experiences, including their interactions with the health care system. In effect, the couples will be asked to tell their "stories". Should topics not emerge that are relevant to the study the interviewer ([name]) will refer to the interview schedule (Appendix 3) and guide the respondents accordingly. In keeping with qualitative research the interviews will be analysed in stages. Early interviews will be analysed and the data used to inform the format of later interviews. So when couples introduce information/areas which are new (i.e. not recorded in the literature or previously known to the researcher) these will be incorporated in to later interviews.

All interviews will be coded by number and anonymised. All interviews will be transcribed verbatim by secretarial staff who are used to dealing with material of a medical/research nature.

3.3. Patient Focus Groups

3.3.1. Recruitment process

This will follow the process for the interviews (§3.2.1) and all patients will be first

approached by the Study Research Nurse in the clinic or by letter from a member of the Clinical care team.

3.3.2. Focus Group Conduct

Couples who express a wish to take part will be contacted by telephone or email (method of contact following their expressed preference) by [name] and offered a choice of times and dates when the group meeting will take place. Immediately prior to the focus group the consent will be discussed and signed consent forms will be obtained. Couples will be reassured regarding confidentiality and anonymity. A copy of the consent form will be given to the participants at this time.

Patients and their partners will be allocated to one of three focus groups (two NHS; one private sector) consisting of six to eight couples per group. Couples will be invited to attend these small group discussions at a suitable venue (St. Mary's Hospital – NHS; Manchester Fertility Services – private sector); the necessary maps and bus routes will be provided. Travel expenses will be reimbursed. The aim is to make these meetings as relaxed and informal as possible. Couples who attend will be greeted warmly and light refreshments will be provided.

The researcher ([name]) will act as group facilitator. An assistant (research associate) will maintain the tape recording equipment and take the necessary field notes. The facilitator will encourage the group to discuss general areas of interest concerning assisted conception treatment to open the session. Gradually, the facilitator will adopt a more interventionist style (Kitzinger, 1995), steering the debate towards topics of interest to the study (see Appendix 4). It is anticipated that these group sessions will last one to two hours. On completion, the couples will be thanked for contributing their time and effort to the project. All those couples who take part will be sent a resume of the main findings from the focus groups.

All group interviews will be coded by number and anonymised. All group interviews will be transcribed verbatim by secretarial staff who are used to dealing with material of a medical/research nature.

3.4. Recording and transcript retention

Interviews and focus groups will be recorded on two portable recorders (digital and standard audio-tape as back-up). After each interview the data will be stored immediately either on the University server (password protected) for digital material or stored in a locked cabinet (audio-tapes) on University premises. The qualitative researcher ([name]) will act as principal custodian for the interview data. Analysed data from the study will be stored for five years.

3.5. Confidentiality

Interviews will be transcribed as soon as possible and all personal names/identifiers will be changed. Thus, after each interview the anonymised recorded data will be emailed to the transcriber. When the interview has been transcribed, this will be emailed back to either the researcher and she will check the transcription back against the recorded interview and make any amendments. The transcriber will be asked to delete her copy of the recorded interview from her computer. All digital recordings/tapes will be destroyed on completion of the study.

All data sets will be assigned a unique code and will only be identified this way in any ensuing reports and publications. Verbatim material reported by participants will be anonymised. This will ensure that selected quotes cannot be linked to individual study participants.

4. Data Analysis

4.1. Statistical analysis

Within each of the cohorts we will use hierarchical logistic regression to develop predictive models for success per transfer cycle for patients receiving SET and DET from both fresh and frozen embryos. Within the DET cohorts we will develop similar models for twinning rates. These models will use aggregated embryo data and be applied to all three data series. Models will be developed which (a) include all potentially prognostic factors as determined from the literature and (b) include factors found to be predictive in the current series using statistical model selection based on the Akaike Information Criterion.

For the single centre and AAP datasets where we have embryo-level data we will utilise the EU model (Speirs *et al*, 1983) and develop models for outcome per cycle which explicitly include recipient and embryo effects (Roberts, 2006; Zhou & Weinberg, 1998). Again models will be developed which (a) include all potentially prognostic factors as determined from the literature along with (centre specific) measures of embryo development and quality and (b) include factors found to be predictive in the current series using statistical model selection based on the Akaike Information Criterion. These models can be fitted using maximum likelihood and (more generally) using an MCMC approach and WinBugs. We have software written in R (R Development Core Team, 2005) which can fit the EU models by direct maximisation of the likelihood and which can include a couple-level random effect. We also have WinBugs (<http://www.mrc-bsu.cam.ac.uk/bugs/winbugs/contents.shtml>) code to fit these models by MCMC methodology, although this latter approach does suffer from slow convergence (Dukic & Hogan, 2002; Natarajan & McCulloch 1998).

We will consider the full range of potential predictive factors, as far as the datasets will allow, and will take care that each variable is included in an appropriate manner. For instance our work with the Manchester data has shown that both age and embryo quality require appropriate semi-parametric methods (that analysis used cubic splines) to capture the complexities of the relationships.

Essential to the modelling process will be the interaction between the statisticians, embryologist and clinicians. Regular discussion between the three groups will ensure that the models remain clinically relevant and will continually inform the modelling process. Statistical model selection methods will be employed, but these will not be used blindly, but in a supervised way informed by clinical knowledge. This interaction has proved essential in obtaining useful models of the Manchester data.

We will give careful consideration to the hierarchical nature of data and within-cycle and within-patient correlations (Ecochard & Clayton, 1998). For the HFEA data, and for combined analyses of the single-centre datasets, this will require consideration of centre effects using appropriate random effect models.

We will also give consideration to potentially more appropriate outcome measures which are derivable from the datasets and which take into account the whole treatment programme. Explicitly we intend to include, where possible, live birth per egg collection and cumulative pregnancy rate from patients with cycles early in each clinic cohort. Due consideration of the (both left and right) censoring of the treatment histories will inform the definition, utilisation and analysis of these endpoints, principally by ensuring rigorous definition of the endpoints and selection of appropriate analysis datasets.

From these models we will be able to predict outcomes for a range of treatment scenarios. In particular the EU models will allow prediction of SET outcomes for those patients who received DET. These predictions will include direct predictions from the models, and also predictions for treatment regimens beyond those encompassed within the datasets. For the latter we will use the parameter estimates from the models, including the estimates of inter-cycle correlations to estimate outcomes for multi-cycle treatment programmes. We will utilise a number of approaches to determine the accuracy of the prediction, both statistical

(bootstrap, cross-validation and training/validation set methods) and internal (comparisons between the data series) and external (comparison with published trial data) comparisons.

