Embryo selection: The ability to select a “top quality” embryo for transfer is crucial to the success of eSET (e.g. De Neubourg *et al*, 2004). Selection is normally made on morphological grounds, with different scoring systems in use in different centres. There is considerable interest in selection criteria (e.g. Ebner *et al*, 2003), and in alternative markers to morphology (e.g. Brison *et al*, 2004). Our own Manchester-Leeds-York collaboration (following on from Brison *et al*, 2004) is currently conducting a multicentre study of the use of amino-acid profiles in the spent culture medium as a marker of embryo quality. Treatment policies on the length of culture of fertilised embryos, the day of transfer, and the use of cryopreservation differ between centres, thus different centres will have differing numbers of embryos at different stages from which to select. To our knowledge no comparative or modelling studies have been undertaken which consider the impact of different cryopreservation/selection policies and it is crucial to capture this in any assessment of the impact of SET.

Prognostic factors: Retrospective studies have identified a number of patient, embryo and treatment factors that are associated with treatment success. Female age and previous reproductive success are the principal maternal predictors, along with basal FSH levels and duration of infertility (e.g. HFEA, 2005; Templeton *et al*, 1996; Kupka *et al*, 2003). Embryo quality is clearly important, as assessed by morphology (Ebner *et al*, 2003). Smoking, both maternal and paternal, is associated with poor outcomes, but the evidence for other lifestyle factors is weak (Klonoff-Cohen, 2005).

Economics: Few studies looking specifically at eSET from the economic perspective have been reported (reviewed in Bergh, 2005). From a societal perspective, these indicate that the savings in health costs associated with twin pregnancies may offset the direct additional costs of the repeat SET cycles required to maintain the same take home baby rate. However in many cases the direct costs of treatment are borne by the patients, whilst the costs associated with multiple births are (in the UK) met within the NHS. A recent publication (Ledger *et al*, 2006) has studied the impact of multiple births from a UK perspective. In addition there are less readily quantifiable costs associated with a potential requirement for extra treatment cycles per baby in eSET.

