2.4. Retrospective Cohort studies (objectives 1 & 2)

We will undertake a series of linked cohort studies to determine factors associated with

success and twin rates in SET and DET. Our collaboration will include the full spectrum of patient settings including NHS-funded patients attending a centre offering only NHS treatment (SMH), private patients attending a fully-private clinic (MFS) and NHS-funded, fee-paying NHS patients and self funded (private) patients within NHS clinics (Leeds, Birmingham, Liverpool, Newcastle). The centres included cover a range of policies on SET, embryo selection and freezing. By considering the full range of patients, we ensure that our results can be generalised to patients treated within the NHS in the likelihood that future policy developments, such as the recent NICE recommendation, lead to changes in the demographic and clinical characteristics of NHS patients.

Specifically we will collate data from the following sources:

1. Data from the national HFEA register. This provides outcome data on each embryo-replacement cycle conducted in the UK, with a useful, but not exhaustive set of patient, partner and cycle factors. However this dataset contains no embryo-level data. The data are anonymised, but records relating to the same couples are linked. For these analyses we would initially propose to use a 2000-2005 cohort, extending this if required. There are issues about data quality in such databases, but the Historic Audit project (due to be completed early 2006) will at least ensure the quality of the data in cycles which generated a pregnancy. [Collaborator: [name]]
2. A collection of single-centre information-rich datasets with embryo quality measures on all transferred embryos. We will extract a cohort with full outcome data for treatments completed in the 2000-2005 timeframe. We currently have 6 centres who have indicated they are willing to provide the necessary data, covering a range of practice and funding models, and which provide sufficient data for the purposes.
 - a. We are currently analysing a large cohort (1998-2003) from the St Mary's Assisted Conception Unit in Manchester - currently 1989 cycles from 1388 patients, with detailed treatment, prognostic and outcome data. We will update these data to give approximately 2400 cycles. These are entirely NHS-funded patients with a high rate of elective SET. [[name] and [name]]

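### The six-centre data largely sit inside the HFEA register, so agreement between the two series is not an independent check of prediction accuracy

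*Protocol*

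**What the plan says.** Section 2.4 of the protocol defines three data series.

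- **Series 1, HFEA register (item 1).** It holds "outcome data on each embryo-replacement cycle conducted in the UK". On the period, the protocol says "we would initially propose to use a 2000-2005 cohort, extending this if required".
- **Series 2, six single-centre datasets (item 2).** "We will extract a cohort with full outcome data for treatments completed in the 2000-2005 timeframe". All six are UK clinics: St Mary's (SMH) and MFS in Manchester, Leeds, Liverpool, Newcastle and Birmingham.
- **Series 3, amino acid embryo study (item 3).** It has 400 double and more than 100 single transfers, with recruitment due to finish by August 2006. Section 1.1 says that a Manchester-Leeds-York collaboration "is currently conducting a multicentre study of the use of amino-acid profiles in the spent culture medium as a marker of embryo quality".

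Section 4.1 fits the aggregated logistic models to all three series. It then lists the ways in which prediction accuracy will be determined: bootstrap, cross-validation and training/validation sets, together with "internal (comparisons between the data series) and external (comparison with published trial data) comparisons". Neither 4.1 nor the data collation list in 3.1.1 mentions that cycles may appear in more than one series.

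**The concern.** Agreement between two data sources supports a prediction model to the extent that the sources could have disagreed. Where one source contains the other, part of the agreement is built in. Two things are at stake.

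1. A model developed on the register and then checked on the centres is scored on cycles that helped to fit it, and factors chosen by AIC are partly re-tested on the records that selected them.
2. If the six centres differ from the rest of the UK, the register figure already includes them, so the visible difference is smaller than the real one. That difference bears directly on whether the predictions carry over to other clinics.

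**Working it through.** **The plan's own figure.** Section 2.8 gives a minimum of 4000 cycles from 40 variables, 10 to 20 events per variable and a 20% success rate. 40 × 20 / 0.20 = 4000, so it reproduces at the upper rule of thumb. The overlap point does not depend on it, but the inputs are used in step 4.

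**1. Size of the overlap.** Centre counts from section 2.4: SMH 2400, MFS 2000, Leeds 4000, Liverpool 4000, Newcastle 2500, Birmingham 2400.

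n = 2400 + 2000 + 4000 + 4000 + 2500 + 2400 = 17,300.

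Every one of these that is a replacement cycle in 2000-2005 is also in series 1. There are exceptions. The existing SMH cohort starts in 1998, and section 3.1.1 leaves the site windows open ("The time period to be collected for each site (may vary due to logistical issues"). Even if all 2400 SMH cycles fell outside the register window, which is extreme, 14,900 would remain.

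**2. Dilution of a true difference.** Let N be the register size, f = n/N, and let the mean outcomes be m_c in the six centres and m_r elsewhere. The register mean is f·m_c + (1 − f)·m_r, so

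observed gap = m_c − register mean = (1 − f)(m_c − m_r).

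**3. Built-in agreement.** For crude rates with common variance σ², Var(centres) = σ²/n and Var(register) = Cov = σ²/N. Hence the correlation is √f instead of 0. The variance of the difference is σ²(1/n − 1/N), against σ²(1/n + 1/N) for separate samples of the same sizes, so the SD ratio is √((1 − f)/(1 + f)).

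The protocol does not state N. The values below are assumptions.

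| Assumed N | f | Share of true gap visible (1 − f) | Correlation √f | SD ratio |
|---|---|---|---|---|
| 60,000 | 29% | 71% | 0.54 | 0.74 |
| 100,000 | 17% | 83% | 0.42 | 0.84 |
| 150,000 | 12% | 88% | 0.34 | 0.89 |
| 200,000 | 9% | 91% | 0.29 | 0.92 |
| 250,000 | 7% | 93% | 0.26 | 0.93 |

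A simulation at N = 100,000 gave a correlation of 0.41, against 0.42 from the formula. With 14,900 shared cycles and a similar SMH success rate, the visible share would be 75% at N = 60,000 (1 − 14,900/60,000) and 94% at N = 250,000.

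**4. Effect on apparent discrimination.** On the section 2.8 inputs, 17,300 × 0.20 / 40 = 86.5 events per variable, so there is little overfitting for the overlap to hide. A small simulation (15 runs per case) assumed an AUC near 0.67, independent cycles, identical centres and no AIC selection.

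| Check | With overlap | Disjoint |
|---|---|---|
| Centre model on register, N = 60,000: AUC | 0.667 | 0.665 |
| Same: calibration slope | 0.970 | 0.958 |
| Centre model on register, N = 100,000: AUC | 0.665 | 0.664 |
| Centre model on register, N = 200,000: AUC | 0.665 | 0.665 |
| Register model on centres, N = 100,000: AUC | 0.669 | 0.667 |

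The inflation is about 0.002 in AUC or less. Because the centres were made identical, this says nothing about the dilution in step 2.

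**5. Series 3.** About 500 transfers are 500/17,300 = 3% of the centre total, or 500/8,400 = 6% of Manchester plus Leeds (2400 + 2000 + 4000). How many are shared cannot be computed, because neither the start date nor the recruiting clinics are given.

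**The case against.** The protocol labels the between-series comparison internal and nowhere says that the series are independent. It also has resampling, split-sample validation and published trial data, so the comparison is one check among several. The models that carry most weight for predicting single-transfer outcomes, the embryo-uterus (EU) models, need embryo-level data. The register has none, so the HFEA overlap reaches only the aggregated logistic models. Section 4.1 could also be read as comparing separately fitted models rather than scoring one series' model on another's records. Finally, handling of duplicates could be left to an analysis plan or to the data collation plan in 3.1.1.

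Most of this stands, and it limits the weight of the point. It does not remove it. The protocol itself fixes the sources, the common window and the use of between-series agreement to determine accuracy. Calling the check internal does not make nested series informative about each other, and separately fitted models still share records. Resampling within one series does not show how predictions carry over to other clinics.

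A reader might infer three stronger things, which the documents do not support:

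- **That prediction error will be seriously understated.** With this many events per variable, the optimism from shared records is small.
- **That the amino acid study duplicates centre cycles.** Shared sites and a recruitment end in August 2006 make it possible. Without a start date or a list of clinics it remains an inference.
- **That duplicates can never be traced.** Section 3.1.3 lets centres keep a temporary cross-reference list until extraction and validation are finished, so flagging is feasible in that window.

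**Conclusion.** The point holds for the HFEA register against the six centres. By the protocol's own description the centre data, about 17,300 cycles mainly from 2000-2005, are largely a subset of the register, so agreement between HFEA-based and centre-based logistic models is not an independent check. A register model tested on the centres meets its own training cycles, apart from any outside the window, whatever the register's size. A true centre-versus-rest difference would appear at about 71% to 93% of its size. That range rests on assumed register sizes of 60,000 to 250,000 and on nearly all centre cycles being replacement cycles inside the window. The effect on discrimination is probably negligible to small, under the simplifying assumptions in the working. The EU models are not affected by the HFEA overlap. Overlap with the amino acid study is an open question to be checked. Overall this is a modest correction that improves one validation step; it does not undermine the validation plan as a whole.

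**What to change.** In section 4.1, state that for any comparison between HFEA-based and centre-based models, in either direction, the six centres' cycles are excluded from the HFEA set. The centre effects planned for the HFEA data imply that some centre code will be supplied. If the codes are masked, ask the HFEA to flag or exclude the six centres. The full register can still be used for every other purpose.

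For the amino acid study, find out at extraction which clinics recruited and when. If it overlaps series 2, have those clinics flag its participants while the temporary lists still exist, and drop them from series 2 whenever series 3 is used for validation.

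The cost is a sentence or two of wording, one filter or a request to the HFEA, and possibly one flag at extraction. The downside is a slightly smaller HFEA comparison set: N − 17,300, for example 82,700 of an assumed 100,000.
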